#### 8.1 Screening

If a subject fails to meet the eligibility criteria, re-screening is allowed in the cases described in Section 5. Re-screening should occur after a subject has failed screening. A new subject number will be assigned and the site must record the re-screening information in the corresponding eCRF and in IRT.

In the case where the subject meets all inclusion/exclusion criteria but does not meet sputum positivity for pathogenic bacteria, or the sputum sample volume is inadequate (<5mL), a second sputum collection on a separate day during screening is permitted to be performed prior to randomization for further assessment of qualification. Results must be received before randomization.

In the case where the subject meets all inclusion/exclusion criteria but does not meet serum fibringen requirement a second serum fibringen collection on a separate day is permitted to be performed prior to randomization for further assessment of qualification. Results must be received before randomization.

In the case where a safety laboratory assessment at screening is outside of the range specified in the exclusion criteria, the assessment may be repeated once prior to randomization. If the repeat value remains outside of the specified ranges, the subject must be excluded from the study and considered as screened failed.

If a subject re-screens for the study, then the subject must sign a new ICF and be issued a new subject number prior to any screening assessment being conducted. The investigator/qualified site staff will record if the subject was re-screened on the re-screening eCRF along with the screening number the subject was issued prior to the current screening number. Subjects who have previously screen failed once or twice due to sputum CFU level being too low under the original protocol with or without fibringen being too low, but who had sputum positive for at least one potentially pathogenic organism, may be re-screened for the study once using the updated inclusion/exclusion criteria from the protocol amendment v02 (inclusive of version 01 changes). If this screen fail subject had a HRCT as part of original screening activities, a repeat HRCT is not required unless more than 12 months have passed since the prior HRCT.

The date of the new informed consent signature must be entered on the informed consent eCRF corresponding to the new screening subject number. For re-screening, all screening assessments must be performed per protocol.

Information on what data must be collected for screening failures and further information on re-screening is outlined in the Site Operations Manual.

#### 8.1.1 Information to be collected on screening failures

Subjects who sign an informed consent but fail to continue into the Baseline/Day 1 visit for any reason will be considered a screen failure. The reason for the screening failure will be entered on the screening disposition page. If the subject fails to be randomized, the IRT must be notified within 2 days of the screen fail that the subject was not randomized.

Information on what data must be collected for screening failures and further information on re-screening is outlined in the Site Operations Manual.

#### 8.2 Subject demographics/other baseline characteristics

Subject demographic and baseline characteristic data are to be collected on all subjects. Relevant medical history/current medical condition present before signing the informed consent will be recorded. Investigators will have the discretion to record abnormal test findings on the appropriate eCRF whenever, in their judgment, the test abnormality occurred prior to the informed consent signature.

Country-specific regulations should be considered for the collection of demographic and baseline characteristics in alignment with eCRF.

Details are outlined in the Site Operations Manual.

#### 8.3 Efficacy / Pharmacodynamics

The efficacy assessments selected are standard for this indication/subject population.

Blood and sputum samples will be collected and evaluated in all subjects at the timepoints defined in the Assessment Schedule (Table 8-1). Follow instructions outlined in the Site Operations Manual regarding sample collection, numbering, processing, and shipment. Number of samples/blood draws and total blood volume collected will not exceed those stated in the protocol.

For all completed scales/questionnaire described below, the Investigator will be required to review and examine responses which may indicate potential AEs or SAEs. The investigator should review not only the responses to the scale but also for any unsolicited comments written by the subject. If the occurrence of AEs or SAEs is confirmed, the investigator / physician should record the events as per instructions given in Section 9.

#### 8.3.1 Spirometry

Spirometry testing will be performed according to the ATS/ERS guidelines (Miller et al 2005a; Miller et al 2005b) at screening to assess subject eligibility for the study and at the visits detailed in the assessment schedule in Table 8-1.

The spirometry evaluation should be performed at the site prior to the morning investigational drug intake and the daily COPD maintenance background therapy, as pre and postbronchodilator. Refer to instructions for medication washouts in Table 8-1.

Bronchodilator challenge will only be performed during the screening visit to establish data to meet inclusion/exclusion criteria related to asthma. Spirometry without bronchodilator challenge will be performed at all other visits.

The spirometry equipment used during the trial will be provided to all study sites by a Central Spirometry vendor. The equipment must meet or exceed the minimal ATS/ERS recommendations for diagnostic spirometry equipment as defined in the guideline provided by the vendor. Calibration of the spirometry equipment is mandatory on all visit days and must be performed before the first subject spirometry test is assessed. All calibration reports and subject spirometry reports should be stored as source data.

The same spirometry equipment should be used for all assessments performed by a subject. A limited number of qualified staff, as designated by the investigator, will evaluate all subjects

at all visits throughout the entire trial at each site. Where possible the same technician should perform all maneuvers for an individual subject. All staff conducting the spirometry tests must have received appropriate training which must be documented.

A Spirometry Manual will be provided to all sites as separate document.

All spirometry assessments will be undergoing review by a central overreader. Acceptability of a spirometric assessment attempt depends on the overreader's judgement for compliance with and acceptability according to the ATS/ERS criteria.

#### 8.3.2 **High Resolution Computed Tomography (HRCT)**

High Resolution Computed Tomography (HRCT) will be performed at Screening and at Day 84. The HRCT performed during screening should be performed toward the end of the screening period after most or all other screening assessments have been confirmed. By conducting the HRCT close to last in screening procedures, those subjects who fail screening will not be exposed to unnecessary radiation as HRCT would no longer be needed. The acquisition will include inspiratory and expiratory image sets at both assessment time points. Protocol specific requirements of the HRCT and machine settings will be provided to all sites as part of a separate Imaging Manual. Additionally, the imaging vendor will provide centralized review of the HRCT scans. Screening HRCT data are not required to define subject eligibility.

In summary, evaluation of the HRCT scans will be used to assess extent of:

- airway structure and function for evaluation of change from Screening / Baseline compared to Day 84
- Commercially Confidential Information

Note: The coded medical images will be used primarily for analysis as described in this protocol; however, the images may also be used for the development and evaluation of new analysis methods directly related to the area of research that this study covers.

#### 8.3.3 Appropriateness of efficacy assessments

Not applicable.

#### 8.3.4 Fibrinogen

Fibringen is a glycoprotein, which is the most abundant clotting factor in plasma. Elevated levels of fibrinogen among subjects with COPD were found to be associated with more frequent/more severe outcomes commonly used as endpoints in investigations of COPD (Mannino et al 2015). For details on the collection, handling and storage/shipment of samples, refer to the Laboratory Manual. Samples will be collected at the time points defined in the Assessment Schedule (Table 8-1).

# Commercially Confidential Information

#### 8.3.6 **Bacterial load**

Sputum samples will be collected for analysis of pathogenic bacterial colonization (CFU/mL)(H influenzae, H parainfluenzae, P aeruginosa, S pneumoniae, S aureus, Moraxella

catarrhalis, Enterobacteriaceae, Stenotrophomonas maltophilia, Burkholderia species, and

Achromobacter species or any potential pathogenic bacteria measured by dilution/outgrowth. Any organism that is to be included and that is not included in the list of the protocol defined pathogens should be discussed on a case by case basis with the Novartis Medical Expert.

Depending on different laboratories, the unit of bacterial load CFU/mL is considered equal to CFU/g.

In addition, 16S sRNA based analysis will be performed to provide microbial profiling. The analysis will be performed on remaining sputum samples collected for microbiology assessment.

Spontaneous sputum collection: on scheduled sputum collection visits, including Screening and Baseline at least one sputum specimen should be collected in the morning before breakfast and at pre-dose time-point during the treatment period. In case subjects can't produce enough sputum on the individual scheduled visits, they can come back up to 3 days after the scheduled visits to try to produce sputum sample. If two spontaneous sputum collection attempts are still not satisfactory, an investigator may take decision to collect sputum sample after induction by the inhalation of saline (please refer to the Lab Manual

Treatment emerging pathogens will be determined at all visits.

Microbiological analyses, including bacterial colonization and bacterial load profiling, will be performed centrally at a qualified microbiology laboratory.

Commercially Confidential Information

Finally, all sputum samples must be of good quality, according to the quality criterion as specified in Laboratory Sputum Collection Manual. If the sample is determined to be a suboptimal, the site's staff should be contacted immediately and a request should be made for a new sample. Details on the collection and shipment of samples, generation of data and reporting of results by the microbiology laboratory are provided in the Sputum Collection Manual.

## 8.4 Safety

Safety assessments are specified below with the assessment schedule detailing when each assessment is to be performed.

For details on AE collection and reporting, refer to the AE section (Section 10.1.1).

The methods, assessment, specification, and recording for each assessment will be detailed in the SOM.

Assessment	Specification
Physical examination	A complete physical examination will include the examination of general appearance, skin, neck (including thyroid), eyes, ears, nose, throat, lungs, heart, abdomen, back, lymph nodes, extremities, vascular, and neurological. If indicated based on medical history and/or symptoms, rectal, external genitalia, breast, and pelvic exams will be performed.
	A short physical exam will include the examination of general appearance and vital signs (blood pressure [SBP and DBP] and pulse). A short physical exam will be done at all visits starting from Day 1 except where a complete physical examination is required (see above).
	Information for all physical examinations must be included in the source documentation at the study site. Clinically relevant findings that are present prior to signing informed consent must be recorded on the appropriate eCRF that captures medical history. Significant findings made after signing informed consent which meet the definition of an Adverse Event must be recorded as an adverse event.
Vital signs	Vital signs include BP and pulse measurements. After the subject has been sitting for five minutes, with back supported and both feet placed on the floor, systolic and diastolic blood pressure will be measured three times using an automated validated device, e.g. OMRON, with an appropriately sized cuff. The repeat sitting measurements will be made at 1 - 2 minute intervals and the mean of the three measurements will be used. In case the cuff sizes available are not large enough for the subject's arm circumference,

# 8.4.1 Laboratory evaluations

Height and weight

A central laboratory will be used for analysis of all specimens collected. Details on the collections, shipment of samples and reporting of results by the central laboratory are provided to investigators in the Laboratory Manual. Laboratory assessments will be performed in the visits specified in Table 8-1.

used.

measured.

a sphygmomanometer with an appropriately sized cuff may be

Height in centimeters (cm) and body weight (to the nearest

0.1 kilogram (kg) in indoor clothing, but without shoes) will be

Clinically notable vital signs are defined in Section 16.1.

Clinically significant abnormalities must be recorded as either medical history or adverse events as appropriate. All subjects with laboratory tests containing clinically significant abnormalities should be followed regularly until the values return to within the normal ranges or until a valid reason other than drug-related adverse experiences is identified, even after the medication has discontinued. Clinically notable laboratory findings are defined in Section 16.1.

All abnormal lab results must be evaluated for criteria defining an adverse event and reported as such if the criteria are met. For those lab adverse events, repeated evaluations are mandatory until normalization of the result(s) or until the result is no longer considered to be clinically significant.

Laboratory evaluations

Table 8-2

Test Name
Hematocrit, Hemoglobin, Platelets, Red blood cells, White blood cells, Differential (Basophils, Eosinophils, Lymphocytes, Monocytes, Neutrophils)
Albumin, Alkaline phosphatase, ALT, AST, Gamma-glutamyl-transferase (GGT), high-sensitivity C-reactive Protein (hs-CRP), Lactate dehydrogenase (LDH), Bicarbonate, Calcium, Magnesium, Phosphorus, Chloride, Sodium, Potassium, Creatinine, Creatine kinase, Direct Bilirubin, Indirect Bilirubin, Total Bilirubin, Total Cholesterol, LDL, HDL, Total Protein, Triglycerides, Blood Urea Nitrogen (BUN) or Urea, Uric Acid, Amylase, Lipase, Glucose (fasting)
Microscopic Panel (Red Blood Cells, White Blood Cells, Casts, Crystals only if abnormalities on the macroscopic panel (dipstick) are detected)
Macroscopic Panel (Dipstick) (Blood, pH, Protein, Specific Gravity)
Prothrombin time (PT) / International normalized ratio [INR]), Partial thromboplastin time (PTT), Activated partial thromboplastin time (APTT)
Serum / Urine pregnancy test (refer to 'Pregnancy and assessments of fertility' Section 8.4.3)

# 8.4.2 12-lead Electrocardiogram (ECG)

Triplicate 12-lead ECG will be collected at the time points indicated in Table 8-1.

PR interval, QRS duration, heart rate, RR interval, QT interval, QTcF will be assessed.

Where clinical decisions are based on the QT interval, the length of the QT interval is to be calculated according to the Fridericia QT correction formula (QTcF).

As applicable, QTcF may be calculated at the clinical site, unless auto-calculated by the ECG machine.

Clinically significant abnormalities must be reported as adverse events.

Additional details pertaining to ECG collection and reporting are included in the SOM.

The preferred sequence of cardiovascular data collection during study visits is ECG collection first, followed by vital signs, and blood sampling. A minimum 3 minutes rest period from the beginning of ECG assessments to the start of spirometry maneuvers must be observed at all times.

For each ECG performed, original traces and identical duplicate traces should be printed. Each ECG will be sent electronically for central review directly from the ECG machine. Two identical duplicate print-outs will be generated and kept at the investigator site as source documentation and as back up for submission to the central laboratory in case of problems with the electronic transmission. Each print-out will be kept at the investigator site and will be dated and signed. The subject's number, the date, actual time of the tracing and study code must appear on each page of the tracing. Clinically significant abnormalities must be recorded on the eCRF as either medical history/current medical conditions or adverse events as appropriate.

### 8.4.3 Pregnancy and assessments of fertility

See the Assessment schedule Table 8-1 for timing of the protocol required pregnancy testing; additional pregnancy testing may be performed to meet local requirements. A positive urine pregnancy test requires immediate interruption of study treatment until serum β-hCG is performed and found to be negative.

Refer to Section 10.1.4 for details on Pregnancy reporting.

#### 8.4.4 COPD Exacerbation

Symptom-defined COPD exacerbations identified by the EXACT-PRO instrument (EXACT-PRO-defined exacerbations) are defined as a persistent increase from baseline in total EXACT-PRO score of ≥9 points for 3 days or ≥12 points for 2 days. Whenever the EXACT-PRO diary data suggest that the subject symptoms are worsening according to the above definitions, the diary will trigger an alert advising the subject to contact the site.

A healthcare resource utilization (HCRU)-defined exacerbation is defined as an acute worsening of respiratory symptoms (consisting of at least two of the following symptoms: dyspnea, cough, sputum volume, sputum purulence, chest tightness or wheeze) that requires a change in treatment. HCRU exacerbations are defined as moderate if leading to treatment with systemic glucocorticosteroids and/or antibiotics, and as severe if leading to hospital admission or emergency room (ER) visit lasting >24 h in addition to treatment with systemic glucocorticosteroids and/or antibiotics. Mild HCRU exacerbations are events that can be managed with an increase in usual medication and without the addition of systemic therapy.

Exacerbation therapy is at the discretion of investigators. Suggested therapy includes 5 days of oral prednisolone (or equivalent) 40 mg/day and/or an oral 7 day course of amoxicillin 500 mg t.i.d. (alternatively amoxicillin/clavulanic acid 625 mg t.i.d. or clarithromycin 500 mg b.i.d.) (GOLD 2018).

Subjects who develop a COPD exacerbation between screening and prior to treatment will be screen failed but will be permitted to be re-screened after a minimum of 2 weeks after exacerbation SOC therapy has been stopped. (see Section 5). Scheduled spirometry should not be performed during an exacerbation until it has completely resolved, therefore any scheduled visits that include spirometric assessment should be postponed until the subject has recovered. Visits that do not include spirometric assessment can go ahead as planned. Of note, budesonide and fluticasone are sensitive substrates of CYP3A. Where administered systemically for a COPD exacerbation, efficacy and safety of these drugs should be carefully monitored (see also Section 6.2 for further details).

In case of exacerbation alerts, subjects will need to visit the Site as soon as reasonably possible and be assessed to confirm the exacerbation. This visit will be considered as an unscheduled visit.

# **Commercially Confidential Information**

Subjects experiencing a moderate exacerbation during the treatment period will continue with their study treatment along with the standard of care (SOC) therapy for exacerbation (i.e. antibiotics and/or systemic corticosteroids). In case subjects are treated with antibiotics for their moderate exacerbation, subjects will have to come back to the site for another unscheduled visit approximately 2 weeks after last intake of their antibiotics, as a follow-up visit to provide sputum and blood samples. If the follow-up visit occurs within approximately 1 week from the next study visit, subjects can come back directly to the planned visit as per Assessment schedule and proceed with the respective procedures as per protocol for this study visit day.

Subjects experiencing a severe exacerbation who need to be treated in the hospital will be discontinued of study treatment during this time, with the possibility to restart study treatment approximately 2 weeks after the last day of their antibiotics intake for their exacerbation. Those subjects who took antibiotics should also provide sputum and blood samples before restart with study treatment. Subjects who were not treated with antibiotics during their hospital stay can restart with study drug directly after hospital stay.

Exacerbation start time is considered as the day the subject is provided with antibiotics or systemic corticosteroids. Exacerbation end date is considered as the day after the last intake of antibiotics or systemic corticosteroids. In case of intake of both antibiotics and systemic corticosteroids, start and end date of the exacerbation refers to the start and end date of the antibiotics intake.

Finally, if an exacerbation happens after EOS visit, subjects will be treated at the discretion of the subject's physician.

Following treatment for the exacerbation, the subject will be expected to continue in the study provided the investigator considers that the subject can safely return to their pre-exacerbation medications.

All HCRU-defined exacerbation events and given therapy should be recorded on relevant eCRF pages.

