## 12.4.1 **Definition of primary estimand**

The primary estimand, defined below, quantifies a hypothetical effect of 12 weeks treatment that would have been observed if all subjects remained on their treatment for 12 weeks:

- **Target population**: subjects with moderate to severe COPD with features of chronic bronchitis and a history of exacerbations and treated with any of the combinations of LABA, LAMA, or ICS along with or without macrolides as background therapy
- **Variables of interest**: change from baseline in fibringen after 12 weeks of treatment.
- **Intercurrent events of interest:** 
  - 1. Discontinuation of study treatment or study participation before 12 weeks of treatment
  - 2. Intake of rescue medications or intake of antibiotics before 12 weeks of treatment
- **Summary measure:** mean difference between treatment groups (OBW251 compared with placebo).

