## 12.4.2 Statistical model, hypothesis, and method of analysis

The primary analysis will include all available data from subjects in the PD analysis set.

The fibringen samples taken within 2 weeks after exacerbation or during or after last dose of antibiotics other than macrolide would be set to missing if a valid unscheduled assessment did not happen at that time point for the primary analysis.

The primary analysis will be performed using a one-sided test at alpha=0.1 (two-sided 80% confidence intervals) and estimated treatment difference (QBW251-Placebo) at week 12 will be reported along with associated 80% confidence intervals.

The comparison of QBW251 to placebo will be evaluated by testing the following null hypothesis  $(H_0)$  versus the alternative hypothesis  $(H_1)$ :

H0: There is no reduction in fibringen from baseline after 12 weeks of treatment in QBW251 compared to placebo

H1: There is a reduction in fibrinogen from baseline after 12 weeks of treatment in favor of QBW251 compared to placebo.

The change from baseline in fibrinogen is assumed normally distributed. A MMRM will be fitted to the changes from baseline in fibringen for all time points until Day 84 visit including the fixed factors and covariates but are not limited to the following:

- treatment group
- visit/time

- treatment group by visit/time interaction
- smoking status
- baseline fibringen value by visit/time interaction.

If normality assumptions are not met, then the fibringen data may be log transformed.

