6.1.1 Variables

The primary estimand, defined below, quantifies a hypothetical effect of 12 weeks treatment that would have been observed if all subjects remained on their treatment for 12 weeks:

- **Target population:** subjects with moderate to severe COPD with features of chronic bronchitis and a history of exacerbations and treated with any of the combinations of LABA, LAMA, or ICS LABA/LAMA, LABA/ICS or LABA/LAMA/ICS along with or without macrolides as background therapy.
- Variables of interest: change from baseline in fibrinogen after 12 weeks of treatment.
- Intercurrent events of interest:
 - 1. Discontinuation of study treatment or study participation before 12 weeks of treatment
 - 2. Intake of antibiotics to treat exacerbations (other than macrolides taken as background medication)
 - 3. Intake of systemic corticosteroids to treat exacerbations.
 - 4. Use of rescue medications before 12 weeks of treatment with study drug or placebo is complete
- **Summary measure:** mean difference between treatment groups (QBW251 compared with placebo).

Novartis	Confidential	Page 12 of 20
SAP Amendment 1		Study No. CQBW251B2202

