6.1.3 Statistical model, assumptions and hypotheses

The primary analysis will include all available data from subjects in the PD analysis set.

The fibrinogen samples taken within 2 weeks after exacerbation or during or after last dose of antibiotics other than chronically administered macrolide would be set to missing if a valid unscheduled assessment did not happen at that time point for the primary analysis.

The primary analysis will be performed using a one-sided test at alpha=0.1 (two-sided 80% confidence intervals) and estimated treatment difference (QBW251-Placebo) at week 12 will be reported along with the associated 80% confidence intervals.

The comparison of QBW251 to placebo will be evaluated by testing the following null hypothesis (H_0) versus the alternative hypothesis (H_1) :

H₀: There is no reduction in fibrinogen from baseline after 12 weeks of treatment in

QBW251 compared to placebo.

H1: There is a reduction in fibrinogen from baseline after 12 weeks of treatment in favor

QBW251 compared to placebo.

The change from baseline in fibrinogen data is assumed to be normally distributed. A MMRM will be fitted to the changes from baseline in fibrinogen for all time points until Day 84 visit including the fixed factors and covariates but are not limited to the following:

- Treatment group
- Visit/Time
- Treatment group by time interaction
- Smoking status
- Baseline fibrinogen value by time interaction.

If normality assumptions are not met, then the fibrinogen data may be log transformed.

Sensitivity analyses:

Novartis	Confidential	Page 13 of 20
SAP Amendment 1		Study No. CQBW251B2202

Supportive analyses:

Supportive analyses will be performed on subjects whose fibrinogen levels or bacterial load collected at the visits during the study based on the different baseline treatments like LABA, LAMA, or ICS using repeated measures model similar to primary analyses.

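### The documents give two fibrinogen exclusion windows around an exacerbation, and the antibiotic-dated one can keep values taken on or soon after systemic corticosteroids, an intercurrent event in the SAP

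*Protocol*

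**What the plan says.** Protocol 8.4.4 (COPD Exacerbation) dates exacerbations by therapy. The general rule is: "Exacerbation end date is considered as the day after the last intake of antibiotics or systemic corticosteroids". If both classes are taken, the "start and end date of the exacerbation refers to the start and end date of the antibiotics intake".

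The deletion rule for the primary endpoint stands in Protocol 12.4.2 and, almost unchanged, in SAP 6.1.3. The SAP version removes the following: "The fibrinogen samples taken within 2 weeks after exacerbation or during or after last dose of antibiotics other than chronically administered macrolide". It does so only "if a valid unscheduled assessment did not happen at that time point". Neither version names corticosteroids.

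The estimand is hypothetical. Besides discontinuation, Protocol 12.4.1 lists one intercurrent event: "Intake of rescue medications or intake of antibiotics before 12 weeks of treatment". SAP 6.1.1 extends the list and adds, as its third event, "Intake of systemic corticosteroids to treat exacerbations". SAP 6.1.3.1, on missing values, mentions only rescue medication and antibiotics. Rescue medication in this trial is a short-acting beta agonist and nothing else (Protocol 6.2.3), so that term does not reach corticosteroids.

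Protocol Table 6-2, in its antibiotics row, makes all data missing over the period of standard-of-care (SoC) intake and for 14 days more. Protocol 3.1 and 8.4.4 define SoC for a moderate exacerbation as antibiotics, systemic corticosteroids or both.

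**The concern.** The SAP treats corticosteroid use as an event whose effect should be absent from the estimand, but gives it no data rule of its own. For a subject on both drugs, the only rule in the SAP that could remove affected fibrinogen values runs on the antibiotic's dates. If the corticosteroid starts earlier, the window opens too late; if it ends later, the window closes too early. Protocol 8.4.4 leaves exacerbation therapy to the investigator, so the suggested course lengths do not bound the mismatch.

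Fibrinogen is an inflammation marker and the primary endpoint. Values that the estimand means to set aside could therefore enter the primary comparison. Two programmers working from the same documents could also build different analysis datasets, one from Table 6-2 and one from SAP 6.1.3.

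**Working it through.** There is no sample-size or power figure to reproduce; the check is a count of days.

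**Inputs.** Suggested courses: corticosteroid 5 days, antibiotic 7 days (Protocol 8.4.4). Exclusion tail: 14 days (SAP 6.1.3, Table 6-2). All other course lengths and orders below are assumptions.

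**Two reading assumptions.** SAP 6.1.3 does not say that its exacerbation dates are those of Protocol 8.4.4; I assume so. I also read the 2-week limit as applying after the last antibiotic dose. Taken literally without a limit, every later sample would go, and only the early gap would remain.

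**Formulas.** Day 1 is the first dose of either drug. Let the antibiotic run from a0 to a1 and the corticosteroid from s0 to s1.

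- Antibiotic-dated window: a0 to a1 + 14.
- Days to cover: s0 to s1 + 14.
- Early gap = max(0, a0 − s0); late gap = max(0, s1 − a1).

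| Antibiotic days | Corticosteroid days | Masked | Kept, on corticosteroid | Kept, within 14 days after |
|---|---|---|---|---|
| 1–7 | 1–5 (suggested lengths) | 1–21 | none | none |
| 4–10 | 1–5 | 4–24 | 1–3 | none |
| 8–14 | 1–5 | 8–28 | 1–5 | 6–7 |
| 1–7 | 4–8 | 1–21 | none | 22 |
| 1–7 | 8–12 | 1–21 | none | 22–26 |
| 1–7 | 1–10 | 1–21 | none | 22–24 |
| 1–7 | 1–14 | 1–21 | none | 22–28 |
| 1–7 | 1–28 | 1–21 | 22–28 | 29–42 |

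For the 14-day course the late gap is 14 − 7 = 7 days. A sample taken while on the corticosteroid survives only if that course starts before the antibiotic or runs more than 14 days past its end. Counting the end as the day after last intake moves the upper bounds by one day.

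**The Table 6-2 window.** From min(a0, s0) to max(a1, s1) + 14, no day is left uncovered in any of the eight scenarios.

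**Follow-up sample.** Protocol 3.1 and 8.4.4 time the repeat blood sample from the last antibiotic; Table 8-1 footnote 7 times it from the last SoC intake. In the 14-day example these fall on day 7 + 14 = 21 and day 14 + 14 = 28. Day 21 is 21 − 14 = 7 days after the last corticosteroid dose. SAP 6.1.3 lets a valid unscheduled assessment stand in, without defining valid, so the day-21 sample might be used.

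**Corticosteroid-only exacerbations.** The general rule in 8.4.4 covers the 2 weeks after. Whether samples during the exacerbation are removed is unclear, because the word during in SAP 6.1.3 may attach only to antibiotics.

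**Weight of one value.** With 84 / 2 = 42 completers per arm, one kept value shifted by d moves a raw arm mean by d / 42, about 2.4% of d. The documents give neither d nor the number of such values. SAP 1.4 records that the trial was stopped before completion, so each value may weigh more.

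**The case against.** The strongest reply is that Table 6-2 already is the missing rule: read by SoC intake, it removes every sample at issue. That is right as far as it goes, and a reader who inferred that the documents contain no rule at all would be wrong. But the text sits in the antibiotics row, is not carried into the SAP, and refers to an exacerbation period that 8.4.4 dates by the antibiotic alone. It creates a second window rather than settling which one applies.

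Second, 8.4.4 postpones visits with spirometry until an exacerbation has resolved, and in Table 8-1 the post-baseline fibrinogen draws on Days 28, 56 and 84 all fall on such visits. This stands and makes scheduled samples during an unresolved exacerbation unlikely. It does not cover the 14 days after therapy or the unscheduled samples.

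Third, a reader might infer a bias towards no effect. The documents do not support a direction. They give no effect of systemic corticosteroids on fibrinogen, and Protocol 1.1 says that fibrinogen is raised during exacerbations, so a kept value could err either way. Which arm would have more such values is also unknown.

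Fourth, a reader might extend the point to sputum bacterial load. Nothing here supports that: SAP 6.2.1 ties that window to the end of antibiotics, and SAP 6.1.1 lists corticosteroids for the fibrinogen estimand.

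Protocol 12.4.4 plans a sensitivity analysis that keeps values regardless of antibiotics or exacerbation. It tests a wider inclusion and does not isolate corticosteroid-affected values.

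**Conclusion.** The point holds as an unreconciled conflict. Protocol 8.4.4 with SAP 6.1.3 gives one exclusion window, Table 6-2 gives a wider one, and the SAP's corticosteroid intercurrent event has no matching data rule. The narrower window leaves a gap only when the corticosteroid course starts before or ends after the antibiotic: 7 days in the assumed 14-day and 7-day example, none with the suggested courses started together. This rests on taking the 8.4.4 dates as those meant in SAP 6.1.3. The number of affected subjects, the size of any shift and its sign cannot be obtained from the documents. It is a minor point, worth settling because it concerns the primary endpoint and is cheap to resolve.

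**What to change.** For data handling only:

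- In SAP 6.1.3, run the fibrinogen exclusion window from the earlier start to the later end of antibiotic or systemic corticosteroid intake for an exacerbation, plus 14 days. Keep the exception for stable background macrolides. This agrees with Table 6-2.
- In SAP 6.1.3, state which exacerbation dates apply and what makes an unscheduled assessment valid. In SAP 6.1.3.1, name corticosteroids among the causes of missing values.
- Reconcile Table 6-2, Protocol 8.4.4, Protocol 12.4.2 and SAP 6.1.3 on the window. Reconcile Protocol 3.1, 8.4.4 and Table 8-1 footnote 7 on the timing of the follow-up blood sample.
- Leave the bacterial-load window in SAP 6.2.1 on antibiotic dates.

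The cost is one derivation, using therapy records that Protocol 8.4.4 already requires on the eCRF, made by SAP amendment before database lock. The downside is that a few more fibrinogen values become missing and rely on the missing-at-random assumption.
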